6.3.6 Additional Unscheduled Visits

Subjects will be instructed to return to the site if they experience symptoms of UTI during the four-month study period, or to report an adverse event that requires further evaluation.

The following list of procedures and assessments for the Unscheduled Visits is a guide only. The components of the history and physical examination conducted at this visit will be determined by the Investigator or his/her designee. All history and physical data from this visit should be recorded on the Symptomatic Visit CRF:

1. Focused physical examination, if indicated for assessment of symptoms.
2. Pelvic examination, if indicated for assessment of symptoms. A pelvic examination should be performed for all vaginitis symptoms and should be conducted as follows:
 - a. Examination of the external genitalia.
 - b. Speculum insertion and examination of vagina, fornices and cervix with naked eye. Only water must be used to lubricate the speculum at all study visits. Other lubricants could kill *L. crispatus*.
 - c. Vaginal swab for pH, wet mount, KOH, clue cells and amine test (whiff test) performed in clinic.
 - d. Swab of vaginal fluid to be stored for assessment of vaginal microbiota by DNA amplification.
3. Clean catch urine collection for dipstick, urinalysis, and/or urine culture with susceptibility testing if indicated. Urine testing should be conducted for all urinary symptoms while on study.
4. All diagnoses of UTI are to be recorded on the UTI CRF. Subjects diagnosed with UTI during study participation are to be treated as clinically indicated and should continue to receive study treatment.

If the subject has a new symptom (or increase in the severity of an existing symptom), the AE CRF and if necessary, the SAE CRF, should be completed.

6.3.7 UTI Episodes While On Study

Subjects will be instructed to return to the study site if they have persistent or new urinary symptoms. If a UTI is diagnosed by a non-study physician, medical records for that visit will be obtained in order to document the recurrence of UTI.

All antibiotics used to treat UTI should be recorded on the Concomitant Medications Log.

6.4 Clinical Procedures/Evaluations

6.4.1 Pelvic Examinations

Each subject will be examined in the dorsal lithotomy position in designated examination rooms. Only water must be used to lubricate the speculum at all study visits. Other lubricants could kill *L. crispatus*.

6.4.2 Investigational Product Instructions

At Visit 1 (Randomization Visit), each study subject will be counseled on how to use the applicators. Written instructions for administration, storage and handling will be provided to each study subject (Appendix B), along with a Study Diary to record applicator use times and symptoms throughout the study. Each subject will be instructed to use the applicator on scheduled days, and weekly insertion dates will be marked on the Study Diary, which the subject will take home.

Instructions will be given regarding what to do in the event that the subject forgets to use an applicator on the prescribed day (see Section 6.6).

Subjects will be instructed to defer insertion of applicators on days of heavy menstrual flow.

Information will be reviewed with the study subject at each of the follow-up visits, and study personnel will address any questions or concerns that may arise.

Subjects will be asked to return both used and unused applicators.

6.5 Early Discontinuations

If a study subject should discontinue the study prior to Visit 6, all end of study procedures and CRFs should be completed.

6.6 Missed Applicators

During the initial five-day treatment period, if it is already within eight hours of her next dose, she should skip the missed applicator. The subject should record the missed dose on the Study Diary. After Day 5, if a subject misses an applicator, she should be instructed to use the missed applicator as soon as possible (but no more than four days from the scheduled date) and the date should be recorded on the Study Diary.

6.7 Lost Applicators

Extra applicators will be provided to each subject together with the required 13 applicators. If a subject loses or damages a study applicator, she may take one of the extras provided, as long as the total number of applicators used does not exceed 13. Lost or damaged applicators should be documented on the Study Diary.

6.8 Antibiotic Use While On Study

All subjects who receive antibiotics during the four-month study period for UTI or any other infection may remain on study and continue study treatment. All antibiotic use should be reported on the Concomitant Medication Log CRF.

6.9 Laboratory Procedures

6.9.1 Specimen Collection and Processing

- ***Wet Mount Slides (All Visits):*** Wet mount slides will be evaluated for signs of BV (clue cells), trichomonas and/or candida (yeast). If vaginal symptoms develop during the study, additional wet mounts will be done as indicated. These tests will be done in the clinical laboratory of the UTI Research Unit at the Hall Health Primary Care Center.
- ***Urine Dipstick Testing (All Visits):*** A clean catch urine sample will be tested on site for the presence of red blood cells, white blood cells, nitrite, leukocyte esterase and protein.
- ***Urine Pregnancy Test (Visits 1 and 6):*** A urine sample will be tested on site to confirm the absence of pregnancy.

6.9.2 Laboratory Testing

All testing will be performed in the laboratory of [name]. at the University of Washington.

- ***Urine Hemocytometer (All Visits):*** Will be performed during the study visit at Hall Health. Urine samples will be assessed for red blood cells and white blood cells.
- ***Urine Dipstick (All Visits)*** Will be performed during the study visit at Hall Health. Urine samples will be assessed for LE, nitrite and blood.
- ***Urine Culture (All Visits):*** Cultures of midstream, voided clean catch urine samples will be performed in the lab of [name]. at the University of Washington.
- ***Culture of vaginal specimens for Gram stain (All Visits):*** A sterile swab will be used to collect fluid from the vaginal walls. Gram stain and cultures will be done in the lab of [name]. at the University of Washington.
- ***Lactobacillus culture and rep-PCR for Lactobacillus CTV-05 (All Visits):*** A sterile swab will be used to collect fluid from the vaginal walls. Specimens will be analyzed by culture and rep-PCR in the lab of [name]. at the University of Washington.

- ***E. coli culture (All Visits):*** A sterile swab will be used to collect fluid from the vaginal wall. Specimens will be analyzed by culture in the lab of [name]. at the University of Washington.
- ***Qualitative and/or quantitative DNA amplification of vaginal microbiota:*** A sterile swab will be used to collect fluid from the vaginal walls at each visit and stored. DNA amplification will be performed in the lab of [name]. at the University of Washington.

6.9.3 Compliance Monitoring

The study subject will be questioned at Visits 2-6 regarding her use of the applicators and any symptoms she experienced during or following applicator use.

7 MANAGEMENT OF ADVERSE AND OTHER EVENTS

7.1 Adverse Events

An adverse event (AE) is any untoward and/or unintended sign, including an abnormal laboratory finding, symptom, or disease temporally associated with the use of an investigational product, whether or not considered related to the investigational product. Pre-existing events or conditions that increase in frequency or severity during or as a consequence of use of a drug in human clinical trials will also be considered adverse events. Any medical condition or clinically significant laboratory abnormality with an onset date before the first date of study product administration is considered to be a pre-existing condition and should be documented as such.

In this protocol, pregnancy will be considered to be an AE, and will be followed for outcome.

7.1.1 Adverse Event Recording

Adverse events may include illnesses, discomfort, pain, or any medical problem such as cold symptoms or other complaints. They may be clinically significant laboratory abnormalities, or pre-existing conditions which change in severity or nature during the course of the protocol. All AEs, whether serious or non-serious and whether or not related to the study product, must be recorded on the Adverse Event (AE) page of the case report form. Study subjects will be instructed to call or return to the study clinic if they have any unexpected symptoms.

7.1.2 Adverse Event Grading

Each AE should be graded for severity using the following scale:

- Mild: the subject was aware of the AE, but was still able to do all activities; no or minimal medical intervention/therapy required.
- Moderate: the subject had to discontinue some activities due to the AE; no or minimal medical intervention/therapy required.
- Severe: the subject was incapacitated by the AE and unable to perform normal activities; significant medical intervention/therapy required, hospitalization possible.
- Potentially life-threatening: An adverse event or suspected adverse reaction is considered "life-threatening" if, in the view of either the investigator or sponsor, its occurrence places the patient or subject at immediate risk of death. It does not include an adverse event or suspected adverse reaction that, had it occurred in a more severe form, might have caused death.

7.1.3 Assessment of Causality

Each AE should be assessed for its causal relationship to the study product. The Investigator is responsible for making an assessment of whether or not it is reasonable to suspect a causal relationship between an AE or SAE and the administration of the investigational product. The causality assessment will be reviewed by [name] and the Medical Monitor. The assessment of causality will only be reclassified by the Investigator. "Associated with the use of the drug" means: "There is a reasonable possibility that the experience may have been caused by the drug."

In assessing causality the following should be considered:

- Alternative etiology - Is the AE due to the underlying disease being treated or is the AE a new diagnosis?
- Known relationship – Has the AE been observed before with this investigational product or class?
- Temporal relationship – What was the time of onset and resolution in relationship to the receipt of the investigational product?
- Concomitant medication – Is the AE a known side effect of another medication?
- Re-challenge – Does re-challenge result in recurrence of the AE?

For each AE, an assessment of the relatedness to the test agent should be made using the following scale:

- Not Related: Onset of the AE has no reasonable temporal relationship to administration of the investigational product, a causal relationship to administration

of the investigational product is biologically implausible or the event is attributed to an alternative etiology.

- **Unlikely Related:** Onset of the AE has a reasonable temporal relationship to study product administration and although a causal relationship is unlikely, it is biologically plausible.
- **Possibly Related:** Onset of the AE has a strong temporal relationship to administration of the investigational product, cannot be explained by the subject's clinical state or other factors, and a causal relationship is biologically plausible.
- **Probably or Definitely Related:** Onset of the AE shows a distinct temporal relationship to administration of the investigational product that cannot be explained by the subject's clinical state or other factors, or the AE occurs on rechallenge, or the AE is a known reaction to the product or chemical group, or can be predicted by the product's pharmacology.

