7.5 Regulatory Reporting of Serious Adverse Events

In the event of a fatal or life-threatening SAE, [name] will notify the FDA by telephone or facsimile within seven calendar days of receipt of the report. [name]. will follow all 7-day alert reports with a written IND safety report within 15 calendar days of receipt of the case.

Serious adverse event cases that concern non-fatal, non-life-threatening events which are unexpected and at least possibly related to the study product will be submitted in writing to the FDA as 15-day IND safety reports within 15 calendar days of receipt.

[name] will require Investigators to obtain follow-up information on all SAEs.

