8.4 Study Suspension or Termination

As stated above, any SAE must be reported by the Investigator or designee to [name]. and the Medical Monitor. The study will be suspended if two or more SAEs considered "Possibly" or "Probably" related to the product are reported in any study of LACTIN-V. The study will only be resumed if the Medical Monitor and the FDA agree to do so. Study suspension or termination will be reported to the University of Washington IRB.

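### The Possibly Related grade in 7.1.3 excludes events with a competing explanation, so urinary SAEs can miss the 8.4 suspension count and the 15-day reports in 7.5

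*Combined protocol and SAP*

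**What the plan says.** Section 7.1.3 explains association with the drug as follows: "There is a reasonable possibility that the experience may have been caused by the drug". It lists alternative etiology as one of five considerations for the Investigator, then gives a four-grade scale.

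- **Not Related** has several routes. One is that "the event is attributed to an alternative etiology".
- **Unlikely Related** needs reasonable timing and a link that is plausible but unlikely.
- **Possibly Related** needs strong timing, and the event "cannot be explained by the subject's clinical state or other factors, and a causal relationship is biologically plausible".
- **Probably or Definitely Related** opens with the same exclusion and then offers alternatives: "or the AE occurs on rechallenge, or the AE is a known reaction to the product or chemical group, or can be predicted by", where that last item concerns pharmacology.

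On review of grades, the section says: "The assessment of causality will only be reclassified by the Investigator".

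Three rules use relatedness. Section 8.4 begins "The study will be suspended if two or more SAEs considered" and names the Possibly and Probably grades, counting SAEs from any LACTIN-V study. Section 7.2 suspends or stops the study at two or more product-related SAEs and names no grade. Section 7.5 requires a 15-day FDA report for non-fatal, non-life-threatening SAEs "which are unexpected and at least possibly related to the study product". Section 8.2 provides no independent data monitoring committee; the Medical Monitor and Principal Investigator review safety data.

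**The concern.** A grade called Possibly would normally hold events for which the product is one credible cause among others. That is also what the section's own standard describes. The scale instead makes a competing explanation disqualifying. The conflict matters here because the disease under study supplies such an explanation for the urinary events that a safety rule should be able to detect.

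At stake are the count that suspends the study and the 15-day reports. If the wording pushes urinary SAEs below Possibly, both become less sensitive to them. The Medical Monitor reviews causality but cannot change the grade, and no independent committee stands behind that review.

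**Working it through.** The plan states no figure on this point, so the check is of text and logic, followed by an illustration on stated assumptions.

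**1. Trace one event through the scale.** Take a hospitalization for pyelonephritis shortly after an applicator, with a plausible mechanism and recurrent UTI as a competing explanation.

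- Section standard (reasonable possibility): met.
- Possibly Related: timing and plausibility are met. The exclusion fails if the Investigator accepts that recurrent UTI can explain the event.
- Probably or Definitely, first limb: fails on the same exclusion.
- Probably or Definitely, other limbs: rechallenge is unlikely, because 7.4 and 8.3 stop study treatment after any SAE. Known reaction has little support, because pyelonephritis is not among the LV-001 excess events in 11.1.1 and none occurred in UW/LB-001 (2.2.2.2). The documents describe no pharmacology that predicts it.
- What remains: Unlikely, or Not Related if the event is attributed to the other cause.

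**2. How often a competing explanation is at hand.** Section 10.4 assumes 40% recurrence and a 50% reduction, so 40% and 20% by arm. Women expected to have an on-study UTI:

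- 250 enrolled (10.4): 125 × 0.40 + 125 × 0.20 = 50 + 25 = 75.
- 276 enrolled (4.3, 5.1): 138 × 0.40 + 138 × 0.20 = 55.2 + 27.6 = 82.8, about 83.

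That is 30% of women in either case, all with a UTI history and recent antibiotics.

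**3. Which rules depend on the grade.**

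| Rule | Depends on grade? |
|---|---|
| 8.4 suspension | Yes, Possibly or Probably |
| 7.2 suspension or stop | Yes, but no grade named |
| 7.5 15-day report | Yes, and the event must be unexpected |
| 7.5 7-day report, fatal or life-threatening | No relatedness condition stated |
| 7.2 and 7.4 24-hour SAE report | No |
| 7.4 and 8.3 individual treatment stop | No |

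**4. What under-grading does to a two-event rule.** Let n be the women on active product, r the proportion with a truly related SAE, and s the chance that such an SAE is graded at least Possibly. With p = r × s,

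P(at least 2 counted) = 1 − (1 − p)^n − n·p·(1 − p)^(n − 1).

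Both r and s are assumptions. For n = 125, r = 0.02 and s = 1: 1 − 0.080 − 0.204 = 0.716. For s = 0.5, p = 0.01: 1 − 0.285 − 0.359 = 0.356.

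| r (n = 125) | s = 1 | s = 0.5 | s = 0.25 | s = 0.1 |
|---|---|---|---|---|
| 1% | 0.356 | 0.130 | 0.040 | 0.007 |
| 2% | 0.716 | 0.356 | 0.130 | 0.026 |
| 3% | 0.892 | 0.561 | 0.241 | 0.055 |

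With n = 138 and r = 2% the row is 0.765, 0.402, 0.152, 0.032. The calculation leaves out placebo-arm SAEs and SAEs from other LACTIN-V studies, which 8.4 would also count.

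**The case against.** The strongest reply is that the scale is less closed than it looks. The later limbs of Probably or Definitely are joined by *or* and, as worded, do not carry the exclusion, and Probably counts under 8.4. It would be wrong to infer that an event with a competing explanation can reach neither grade. This stands. It matters most for vaginal events: 11.1.1 lists several, including candidiasis, that were seen in more LACTIN-V than comparison women in LV-001, so the known-reaction limb may apply. Symptomatic BV and yeast are also excluded at Visit 1 (6.2.1.2.2, 6.2.1.3), which removes them from the entry state, although recent antibiotics remain another factor. A claim that vaginal SAEs are shut out to the same degree is therefore not supported. The known-reaction limb helps less with 15-day reports, because those also require the event to be unexpected.

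Second, pyelonephritis is excluded at entry and could be graded as a new diagnosis. That reading is open. But the exclusion refers to clinical state or other factors in general, which is wider than the entry diagnosis, so two investigators could reasonably grade the same event differently.

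Third, a reader might infer that expedited reporting as a whole is impaired, or that the suspension rule could never fire. The documents support neither. Only the 15-day route uses the grade, and a rule that never fires presupposes uniformly literal grading. In LV-002, among women with recurrent UTI, 22 of 30 (73.3%) had an AE graded possibly or probably related, though none was serious and that study's scale is not given.

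Fourth, the genitourinary shares of AEs in LV-005 (69%) and LV-006 (78%), and the 56.4% of LV-003 subjects with related AEs, do not measure how SAEs would be graded here. LV-005 and LV-006 had no SAEs. These figures are not used above.

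Finally, AEs are tabulated by arm regardless of causality (10.10.5) and UTI is compared by arm as the primary endpoint. Those end-of-study comparisons are unaffected, but they do not replace a rule that acts during the trial.

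**Conclusion.** The concern holds for urinary SAEs, and for two uses of the grade: the 8.4 count and the 15-day reports in 7.5. Section 7.1.3 contradicts itself, because an event can meet its reasonable-possibility standard and still be barred from Possibly Related. The alternative limbs of the higher grade are unlikely to rescue a pyelonephritis, and no one but the Investigator can correct the grade.

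The size cannot be read from the documents. On the assumptions above (r of 1% to 3%, 125 active-arm women), grading half of truly related SAEs below Possibly lowers the chance of reaching two from 0.36–0.89 to 0.13–0.56. How far s would fall in practice depends on how literally investigators apply the wording. The finding does not extend to all expedited reporting, to vaginal SAEs in the same degree, or to a trigger that cannot fire. It should be corrected before SAEs are graded, since it feeds a suspension rule in a trial without independent monitoring.

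**What to change.** - In 7.1.3, remove the exclusion from Possibly Related so that the grade matches the section's own standard. Keep it in the first limb of Probably or Definitely Related.
- Add that recurrent UTI or recent antibiotics alone do not settle causality, and carry this into the AE form guidance.
- Reconcile the term product-related in 7.2 with the grades named in 8.4, so that both rules count the same events.
- Leave the thresholds in 8.4 and 7.5 as they are; this change concerns only what the grade means.

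The drafting cost is a sentence or two in 7.1.3, a cross-reference between 7.2 and 8.4, and the form guidance. The operating cost is more events graded Possibly, more 15-day reports, and a somewhat higher chance that background or placebo-arm SAEs count towards suspension. That last cost deserves notice: weekly applicators put many events close to a dose, and under 8.4 the study resumes only if the Medical Monitor and the FDA agree.

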7.2 Serious Adverse Events

A serious adverse event (SAE) is any adverse event occurring at any dose that meets the following criteria:

- results in death
- is life-threatening
- requires hospitalization or prolongation of existing hospitalization
- results in persistent or significant disability/incapacity
- is a congenital anomaly/birth defect
- the event was another, important medical event that may not have met the above criteria but based upon appropriate medical judgment, it jeopardized the subject or required medical or surgical intervention to prevent one of the outcomes listed above

Any AE that is serious (whether expected or unexpected) must be reported by facsimile within 24 hours of the Investigator or site staff becoming aware of the event to [name]., and the University of Washington Institutional Review Board. Sites will use Adverse Event Reporting Forms when submitting SAE reports.

It is the responsibility of the Investigator to report all SAEs to the sponsor, to provide the most complete report possible, and to assess each SAE for its relationship to the study product. Each SAE occurring in this study must be followed to resolution.

The study will be suspended or stopped if two or more product-related SAEs are reported.

7.3 Unexpected Adverse Events

An unexpected adverse event is any AE having a specificity or severity not consistent with the current Investigator Brochure.

7.4 Serious Adverse Event Reporting

All serious adverse events (SAEs) must be reported to [name]. and the Medical Monitor as follows:

- Any AE that is serious (whether expected or unexpected) must be reported by facsimile or email to [name]. and the University of Washington Institutional Review Board using the University of Washington Event Reporting Forms within 24 hours of the Investigator or site staff becoming aware of the event.
- All SAE reports should include the Investigator's assessment of the relationship of the event to the study product.

Any subject with an SAE, whether or not considered related to the study product or procedures, will be discontinued from further study treatment.

